#### **B. Safety Endpoint(s):** wound infection and adverse reaction to Dakin's Solution.

#### **Design:**

A.  Basic Science (Bench or Laboratory)	 Pre-Clinical (Animal)	 Clinical (Human) X
B.  Care Report	 Registry	 Study (Trial) X
C.  Retrospective	 Prospective X	
D.  Non-randomized X	 Randomized	
E.  No Control or Sham	 Sham-controlled	 Reference-controlled X
F.  Single-arm X	 Multiple-arms - Specify (#): _____	
G.  Single-center X	 Multiple-centers - Specify (#): _____	

#### **Study Intervention and Duration:**

- A. Retrospective Study: Start Date \_\_\_\_\_ End Date \_\_\_\_\_
- B. Date First Patient (FPI) or Subject (FSI) In: September 22, 2014
- C. Date Last Patient (LPO) or Subject (LSO) Out: September 22, 2015
- D. Total Duration: 1 year to allow time for patient recruitment, quality assurance and analysis.  
Subjects will be followed from admission to their two-week post-operative clinic visit.

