#### **Superficial incisional SSI**

Must meet the following criteria:

Infection occurs within 30 days after any NHSN operative procedure (where day 1 = the procedure date), including those coded as 'OTH'\*

and

involves only skin and subcutaneous tissue of the incision

and

patient has at least one of the following:

- a. purulent drainage from the superficial incision.
- b. organisms isolated from an aseptically-obtained culture of fluid or tissue from the superficial incision.
- c. superficial incision that is deliberately opened by a surgeon, attending physician or other designee and is culture positive or not cultured

and

patient has at least one of the following signs or symptoms: pain or tenderness; localized swelling; redness; or heat. A culture negative finding does not meet this criterion.

- d. diagnosis of a superficial incisional SSI by the surgeon or attending physician or other designee .

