#### **Deep incisional SSI**

Must meet the following criteria:

Infection occurs within 30 or 90 days after the NHSN operative procedure (where day 1 = the procedure date)

*and*

involves deep soft tissues of the incision (e.g., fascial and muscle layers)

*and*

patient has at least one of the following:

- a. purulent drainage from the deep incision.
- b. a deep incision that spontaneously dehisces or is deliberately opened by a surgeon, attending physician\*\* or other designee and is culture-positive or not cultured

*and*

patient has at least one of the following signs or symptoms: fever ( $>38^{\circ}\text{C}$ ); localized pain or tenderness. A culture-negative finding does not meet this criterion.

- c. an abscess or other evidence of infection involving the deep incision that is detected on direct examination, during invasive procedure, or by histopathologic examination or imaging test.

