#### **Study Population:**

This is a prospective cohort study that will be performed at the University of Arizona Medical Center (UAMC), a Level I Trauma center. Patients who undergo emergent surgery for trauma induced enteric injuries

involving the stomach, small bowel, or colon (ex: gun-shot wounds, stab wounds, blunt colon perforation) or the non-traumatic emergent general surgical pathologies involving the above hollow viscera.

Retrospective review of our database over the past 3 years identified total of 276 patients: 157 patients underwent emergent surgery for trauma related colon injuries and 43 patients due to acute perforated diverticulitis. In addition, 76 patients underwent emergent abdominal surgery for perforated viscus excluding colonic pathologies. Based on these results, we conservatively estimate an average of 90 patients per year will require emergent abdominal surgery for perforated viscus. Thus, we anticipate **enrolling 20 patients** over the 1 year period. This will be followed by data collection, follow-up period, data analysis and report/manuscript about research findings.

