### **Subject Exclusion Criteria**

Prisoners

Age<18

Pregnancy

Patients with allergy to Dakin's (sodium hypochlorite) solution

Enrolled in a concurrent ongoing interventional, randomized clinical trial.

This prospectively collected cohort of patients will be compared to the similar historical cohort from 2008-2013. We will review medical charts of the patients admitted to UAMC following the same inclusion and exclusion criteria described above to perform a retrospective review. We will collect the same data points as in prospective cohort.

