### **Procedures Involved in the Human Research:**

We will approach patients upon the diagnosis to consent them for this prospective study. During the process, the details of the trial will be reviewed along with potential risks and benefits, the endpoints of interest and the process by which these endpoints are evaluated. When notified of trial enrollment, the patient or their legal representative will be given the opportunity to withdraw from further data and sample collection. Those who consent will be enrolled to collect data on outcomes, baseline parameters and follow-up period to evaluate efficacy of VeraFlo for management of contaminated abdominal wounds after emergent surgery. VAC with 1/4% Dakin's solution will be placed immediately at the end of the surgery for the first 3 postoperative days, followed by delayed primary closure on postoperative day 4. Wound will be swabbed at the end of surgery before placing the VAC and before skin closure on Day 4. All follow-ups will be performed as a standard of care.

Data collected will include the following: demographics (i.e. BMI), hemodynamic parameters at the time of presentation and operation, source of infection, imaging studies outcomes, lab tests, surgical procedure performed and its duration, vasopressors, estimated blood loss and transfusion records, antibiotics used and duration, comorbidities (Charlson Morbidity Index, APACHE II), trauma registry data, and complications (if any) during their hospital stay and follow-up in clinic, length of stay (in ICU and in hospital), intra-abdominal wound culture, wound closure details, pain level, cost, wound appearance (recorded by photograph), wound culture, infection, time of nursing care.

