#### **Statistical Analysis:**

#### **Sample Size Calculation:**

- A. Event Rate Assumption(s): <5%
- B. Study Group (%): 100%
- C.  Comparator or  Sham Group (%): historic cohort from previous 3 years.
- D. Power Estimation:  95%  90%  85%  80% or Other – Specify: \_\_\_\_%
- E. Evaluable Rate Consideration: Specify: \_\_\_\_%
- F. Sample Size Calculation: 20 Total Number of Subjects. When population is not divided evenly, please specify how it will be divided and rationale for doing so:
- G. Interim Analysis - Sample Size Re-calculation:  Yes  No  Specify rationale:
- H. Number of Centers Projected: 1

This is an observational prospective study with no concurrent arm for comparison; we will use historic data from our center over the last 3 years to analyze results. The advantage of this approach is that there was no change in medical providers among trauma surgeons in the last 3 years. We also have a robust prospectively collected trauma registry that allows performing this analysis. We will identify patients who have undergone emergent abdominal surgery with hollow viscus violations, and had undergone wet-to-dry dressing changes. A Propensity matching analysis will be performed to match patients from the historic cohort to the current patients by demographics, disease severity and laboratory tests. A univariate analysis, independent t-test, and a Kaplan-Meier survival analysis will be performed to compare rate of infection, time-to-closure, and cost analysis.

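### Follow-up ends at the two-week visit, before the 30-day (or 90-day) primary infection window closes, and the historical controls have no stated cut-off day

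*Combined protocol and SAP*

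**What the plan says.** - **Endpoint window.** The primary outcome is the rate of superficial and deep incisional surgical site infection (SSI) by CDC definitions. For superficial SSI the protocol writes "Infection occurs within 30 days after any NHSN operative procedure (where day 1 = the procedure date"; for deep SSI, "Infection occurs within 30 or 90 days after the NHSN operative procedure". Both count the procedure date as day 1.
- **Follow-up.** Study Intervention and Duration, item D: "Subjects will be followed from admission to their two-week post-operative clinic visit".
- **Other provisions.** Procedures Involved in the Human Research says "All follow-ups will be performed as a standard of care" and lists complications in hospital and at clinic follow-up among the data. The Data Collection Flow Sheet has one Clinic Visit column, with no day attached.
- **Controls.** The paragraph on the historical cohort, under Subject Exclusion Criteria, says "We will collect the same data points as in prospective cohort". It gives no day on which the chart search stops.
- **Use of the endpoint.** Statistical Analysis compares infection rates with propensity-matched historical patients. Item A of the sample size section gives "Event Rate Assumption(s): <5" (per cent).
- **Dates.** Item C has "Date Last Patient (LPO) or Subject (LSO) Out: September 22, 2015", exactly one year after first patient in, and item D fits recruitment, quality assurance and analysis into that year. Study Population anticipates 20 patients over the year and then adds: "This will be followed by data collection, follow-up period, data analysis and report/manuscript about research findings".

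**The concern.** An SSI that appears after the two-week visit meets the protocol's definition of the primary outcome, but the plan provides no occasion to record it. The prospective rate is therefore biased low, and setting it against the assumed rate of under 5% is too favourable. Wound infection is also the safety endpoint, so late infections are lost there as well.

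The timing matters for this intervention in particular. Skin is closed on postoperative day 4, and infection under a closed, contaminated wound is what the Introduction says worries surgeons. Most of the endpoint window after closure falls beyond the planned follow-up.

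Two further gaps add to this. With the deep window left at 30 or 90 days, two analysts could report different primary rates from the same charts. With no cut-off for controls, the cohorts may be searched for different lengths of time. Propensity matching on demographics, severity and laboratory tests cannot correct that.

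**Working it through.** The plan gives no figure of its own on this point to reproduce. Its 20 subjects enter below only as a denominator.

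**1. Window coverage.** With day 1 as the procedure date, a visit 14 days after surgery falls on day 15.
- 30-day window: 15/30 = 50% observed, 15 days unobserved.
- 90-day window: 15/90 = 17% observed, 75 days (83%) unobserved.
- Closure on postoperative day 4 is day 5. Days of closed incision observed: 15 − 5 = 10, against 30 − 5 = 25 to day 30 or 90 − 5 = 85 to day 90.

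These are shares of time, not of infections.

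**2. Effect on the recorded rate.** Let L be the share of SSIs that arise after the visit. The documents do not give L; I assume 0.10 to 0.50. Recorded rate = true rate × (1 − L). True rates are the ends of the 14% to 32% range in the Introduction.

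| True rate | Recorded, L = 0.10 | Recorded, L = 0.50 | Expected SSIs in 20: full window | Expected SSIs in 20: recorded |
|---|---|---|---|---|
| 14% | 12.6% | 7.0% | 2.8 | 2.5 to 1.4 |
| 32% | 28.8% | 16.0% | 6.4 | 5.8 to 3.2 |

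Read backwards, a recorded 5% would correspond to a true rate of 0.05/0.9 = 5.6% up to 0.05/0.5 = 10%.

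**3. Chance of a low count.** Binomial, n = 20, true rate 14%:

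| | Full window (p = 0.14) | L = 0.10 (p = 0.126) | L = 0.50 (p = 0.07) |
|---|---|---|---|
| P(0 or 1 SSI), i.e. 5% or less | 0.208 | 0.263 | 0.587 |
| P(no SSI), i.e. strictly under 5% | 0.049 | 0.068 | 0.234 |

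**4. Comparison with controls.** Suppose the treatment has no effect and control charts are read completely to day 30. The apparent risk ratio is then 1 − L, that is 0.9 to 0.5. If control charts also stop at two weeks, both rates are understated and neither meets the stated definition. If charts miss infections that prospective observation finds, the bias can run the other way.

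**5. Calendar.** With last patient out on 22 September 2015, the latest procedure date that reaches day 15 is 8 September (14 days earlier), day 30 is 24 August (29 days earlier) and day 90 is 25 June (89 days earlier). Enrolment over the full year, as Study Population anticipates, would leave the last patients short of the window.

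**The case against.** The mismatch between follow-up and endpoint window is hard to dispute. The fair objections concern what is built on it.

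- **The controls have a window of sorts.** Complications are to be collected over the hospital stay and clinic follow-up, and the controls get the same data points. That fixes the setting but still gives no day, so the gap remains.
- **The CDC source may settle 30 or 90.** Perhaps it assigns the window by procedure; that cannot be checked from the documents. The protocol's own text does not say which applies, and it should.
- **Day 15 is nominal.** Some patients may still be in hospital, or the visit may slip. True, but neither is a planned assessment at day 30 or 90.
- **The sizes rest on an assumption.** They do. The under-5% figure is also a planning assumption, not a success criterion, so the binomial results describe how easily a low rate appears, not a decision error. With the 9.8% that the Introduction reports for delayed closure, 20 patients give 1.96 expected SSIs and the same assumption loses 0.2 to 1.0 of them: fewer events, but the same proportion.
- **Kaplan-Meier is planned.** With recorded event and censoring dates it could handle unequal follow-up up to about day 15. It cannot estimate day-30 risk in a cohort that nobody follows to day 30, and no censoring rule is given.
- **Chart review is an imperfect cure.** It can miss infections treated elsewhere. That limit stands, although it applies by the same method in both cohorts.
- **The calendar point is minor.** It matters only if enrolment runs late; about 90 eligible patients a year are expected for 20 places.

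**Conclusion.** The concern holds and must be fixed before the primary outcome can be reported as defined. Three things follow from the text alone: follow-up ends at about day 15 against a 30-day or 90-day endpoint, the deep window is not chosen, and the controls have no cut-off day. Late infections would enter the prospective record only if found outside the plan, so the bias in that rate is downward. Its size depends on the assumed late share: a relative understatement of 10% to 50% under the range used here. The direction of bias in the comparison with controls is not certain; it would plausibly favour VeraFlo if control charts are read to day 30 or 90. Analysis cannot repair this if the later data are never collected.

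**What to change.** 1. State one window for deep SSI.
2. Amend item D of Study Intervention and Duration, for example: *SSI status will be ascertained by chart review through day 30 for superficial SSI and through the stated window for deep SSI (day 1 = procedure date).*
3. Add to the historical-cohort paragraph: *The same chart-review method and the same cut-off day will be used in the historical cohort.* Report, for each cohort, how many patients have no chart entry after the two-week visit.
4. Reconcile last patient out with the enrolment and follow-up periods in Study Population, so that the last enrolled patient can complete the window.

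The cost is wording, one later chart check for each of 20 patients, reading control charts to the same day, and about 1 to 3 months more calendar time if enrolment uses the full year.

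If follow-up cannot be extended, define the primary outcome as SSI by the two-week visit, truncate the historical cohort at the same day, and state that this is not the full CDC 30-day or 90-day rate. This needs no extra follow-up but departs from the definition the protocol adopts.

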#### **Study Population:**

This is a prospective cohort study that will be performed at the University of Arizona Medical Center (UAMC), a Level I Trauma center. Patients who undergo emergent surgery for trauma induced enteric injuries

involving the stomach, small bowel, or colon (ex: gun-shot wounds, stab wounds, blunt colon perforation) or the non-traumatic emergent general surgical pathologies involving the above hollow viscera.

Retrospective review of our database over the past 3 years identified total of 276 patients: 157 patients underwent emergent surgery for trauma related colon injuries and 43 patients due to acute perforated diverticulitis. In addition, 76 patients underwent emergent abdominal surgery for perforated viscus excluding colonic pathologies. Based on these results, we conservatively estimate an average of 90 patients per year will require emergent abdominal surgery for perforated viscus. Thus, we anticipate **enrolling 20 patients** over the 1 year period. This will be followed by data collection, follow-up period, data analysis and report/manuscript about research findings.

### **Subject Inclusion Criteria:**

Patients 18 years and older

Emergent surgeries involving enteric injuries e.g. traumatic injuries involving stomach, small bowel, or colon; or the non-trauma emergent general surgical pathologies involving the above hollow viscera.

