#### **Potential Benefits to Subjects and/or Society:**

Current literature shows strong independent benefits of using Dakin's solution and the negative pressure VAC therapy for managing open contaminated wounds. The solution and the device have also been shown not to be harmful. Currently, there is no standard management protocol regarding the combined utilization of Dakin's solution with VAC therapy, a capability delivered by the KCI VeraFlo. This study aims to study the utility and safety of using the VeraFlo with 1/4% Dakin's solution in managing contaminated abdominal wounds. If it is associated with less SSI and earlier achievement of wound closure, then this technique may serve to standardize the management of contaminated abdominal wounds. It has the potential to decrease the time and resource spent on managing open abdominal wounds as compared to the most common technique of wet-to-dry dressing changes. In addition, this technique has the potential to drastically improve patient comfort, convenience and satisfaction.

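### The eligibility and control-selection sections do not define the two cohorts alike, and contamination is not a named matching variable, so the SSI comparison may favour VeraFlo by an unknown amount

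*Combined protocol and SAP*

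**What the plan says.** Subject Inclusion Criteria has a trauma limb, "Emergent surgeries involving enteric injuries e.g. traumatic injuries involving stomach, small bowel, or colon", and a non-trauma limb, "or the non-trauma emergent general surgical pathologies involving the above hollow viscera". Apart from adult age, nothing else is required. The exclusions (prisoners, minors, pregnancy, allergy to the solution, another randomised interventional trial) do not touch the state of the wound.

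The text under Subject Exclusion Criteria then says that the historical charts are reviewed "following the same inclusion and exclusion criteria described above to perform a retrospective review".

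The narrative under Sample Size Calculation describes the control pool differently: "We will identify patients who have undergone emergent abdominal surgery with hollow viscus violations, and had undergone wet-to-dry dressing changes". Propensity matching will "match patients from the historic cohort to the current patients by demographics, disease severity and laboratory tests".

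Procedures Involved in the Human Research states: "We will approach patients upon the diagnosis to consent them for this prospective study". It places the device at the end of surgery in those who consent. Potential Benefits states the question as the use of VeraFlo "in managing contaminated abdominal wounds".

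**The concern.** In a single-arm study with historical controls, a common entry definition is the first protection against confounding by case-mix. Here the two cohorts are described in different terms, and the difference concerns something likely to affect SSI risk: how dirty the wound was, and whether the surgeon thought it safe to close.

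Every VeraFlo wound is open because the protocol makes it so. Every control wound was open because it was managed with wet-to-dry dressings, which the Introduction presents as one choice among several. A past patient with little soiling whose skin was closed primarily is not a control under the statistical section. A similar patient today meets the inclusion criterion and, after consent, is counted as treated. If such patients are more common in the VeraFlo cohort, its SSI rate falls without any effect of the device.

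**Working it through.** **1. The three definitions side by side**

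| Section | Applies to | Bowel condition | Wound condition |
|---|---|---|---|
| Subject Inclusion Criteria | VeraFlo cohort | Enteric injury, or emergent pathology involving stomach, small bowel or colon | None |
| Subject Exclusion Criteria | Historical cohort | Same as above | None |
| Sample Size Calculation | Historical cohort | Hollow viscus violation | Wet-to-dry dressing changes |

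The second and third rows describe the same cohort and disagree. Under the second row, controls may include clean and primarily closed wounds. Under the third row they may not include primarily closed wounds. The viscus wording may be only loose paraphrase, but the wet-to-dry condition is a real addition.

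**2. Whether the adjustment covers it**

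The named matching categories are demographics, disease severity and laboratory tests. Contamination and wound class are absent there. They are also absent from the itemised data lists in Procedures Involved in the Human Research and in Information Management. Source of infection and wound cultures are collected and are partial proxies, but neither is named for matching.

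**3. Size, as an illustration only**

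The plan has no figure for this quantity to reproduce. Inputs:
- pH, SSI rate without a treatment effect in the wounds of interest: 9.8% (delayed closure after enteric injury), 14% and 32% (range for emergency abdominal surgery), all from the Introduction.
- pL, SSI rate in low-contamination wounds: 2% (the Introduction's figure for major elective surgery, used as a floor) and 5% (assumed).
- f, share of low-contamination patients present in the VeraFlo cohort only: 10% and 25% (both assumed).

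With no treatment effect, the treated rate is f × pL + (1 − f) × pH, so the shift is f × (pH − pL).

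| pH | f = 25%, pL = 2% | f = 25%, pL = 5% | f = 10%, pL = 2% | f = 10%, pL = 5% |
|---|---|---|---|---|
| 9.8% | 1.95 points | 1.20 | 0.78 | 0.48 |
| 14% | 3.00 | 2.25 | 1.20 | 0.90 |
| 32% | 7.50 | 6.75 | 3.00 | 2.70 |

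For example, 0.25 × (9.8 − 2) = 1.95 and 0.25 × (32 − 2) = 7.50.

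At f = 25% and pL = 2%, the apparent risk ratios are 7.85/9.8 = 0.80, 11.0/14 = 0.79 and 24.5/32 = 0.77.

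In 20 patients, f = 25% is 5 patients. The expected number of infections falls by 20 × 1.20% = 0.24 at the low end and 20 × 7.50% = 1.5 at the high end. The plan's own assumed event rate of under 5% means fewer than 20 × 5% = 1 expected infection.

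**4. A check in the other direction**

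The share needed to reach 5% by case-mix alone, with pL = 2%, is (pH − 5)/(pH − 2). This is 4.8/7.8 = 62%, 9/12 = 75% and 27/30 = 90% for the three values of pH. Case-mix alone would have to be extreme to produce the rate that the plan assumes.

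**The case against.** A reader might infer that controls must be contaminated and that low-risk patients can enter only the treated arm. The documents do not support that.

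- Subject Exclusion Criteria applies the same criteria to the chart-review cohort. On that text alone the two cohorts are eligible on equal terms. This stands, and it turns part of the point into a contradiction between sections.
- A hollow viscus violation sets no threshold of soiling, and it overlaps heavily with enteric injury. This stands: the statistical section does not require contamination of controls either.
- Wet-to-dry is the comparator treatment and cannot simply be dropped. That surgeons closed the cleaner wounds is an inference from the Introduction, which describes closure as surgeon preference and primary closure as taking a chance on infection. It is a reasonable inference, but the documents give no data on it.

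A reader might also infer that nobody checks the wound before the device is placed. The Data Collection Flow Sheet appears to mark eligibility and consent in the operating room as well as earlier, although column alignment is uncertain in the extracted text. The enrolment-process heading refers to predicted contaminated surgery, and its diagram is not available. The attending surgeon identifies eligible patients, the stated aim is contaminated wounds, and the feasibility estimate counts perforated viscus. All of this suggests that contaminated cases were intended. What remains is that the written criterion does not say so.

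The magnitude is also open to challenge. The 14% to 32% range is for emergency abdominal surgery in general, and 2% is an elective rate. The Introduction also gives 4% to 25.2% across hospitals for elective colorectal surgery. With pL = 4% and pH = 9.8%, a 25% share shifts the rate by 0.25 × 5.8 = 1.45 points. With pL = 25.2% the shift would reverse for pH of 9.8% or 14%. No shift in the table should be read as an estimate.

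**Conclusion.** The point holds as an inconsistency between three sections, with a possible bias toward VeraFlo in the primary comparison. The wet-to-dry condition acts on one cohort only, and the planned matching does not name the variable that would correct for it. Matching on disease severity may remove part of the imbalance, but its content is not specified.

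The size is unknown. Under an assumed 25% share and 2% to 5% SSI in low-contamination wounds, the shift is about 1.2 to 2.0 points at the cited delayed-closure rate of 9.8%, and at most 7.5 points at 32%. The lower figures are the more relevant, because both cohorts have wounds left open at first. The direction rests on two assumptions: that primarily closed historical wounds were cleaner, and that cleaner wounds have a lower SSI rate. The point is worth correcting because the correction is cheap. It does not show that the comparison is invalid.

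**What to change.** - Reconcile Subject Inclusion Criteria, Subject Exclusion Criteria and the control description under Sample Size Calculation into one eligibility definition for the comparison: hollow viscus violation with contamination documented in the operative record. Apply it in the same way to the prospective and chart-review cohorts.
- Record wound contamination class in both cohorts, from the operative record, and add it to the propensity-matching variables.
- State wet-to-dry management separately, as the definition of the comparator treatment and not as an eligibility criterion. Some selection by surgeon's choice will remain, and matching on contamination class reduces it without removing it.

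The cost is one extra chart field, some consented patients not counted in the comparison after operative findings, and a somewhat smaller matching pool. Accrual looks safe. Study Population gives 157 + 43 + 76 = 276 patients over 3 years, or 92 a year, which the plan rounds down to 90. Even without the 157 trauma colon injuries, whose perforation status is not stated, (43 + 76)/3 is about 40 a year against a target of 20, before allowing for refusals.
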